10.3.6 Other Safety Analysis

ECOG PS will be presented as contingency tables by time point. Missing data will not be considered as a category and the calculation of frequencies will use the number of non-missing observations.

Any abnormal finding in ophthalmologic examination will be listed for each subject including the following: date of assessment, type of abnormality, whether the patient wears contact lenses, visual acuity and the results from left and right eye if available.

All safety data collected will be provided in by-subject listings.

10.3.7 Medications and procedures

Medications/Procedures will be classified into three categories:

- Prior: defined as medications/procedures with start date before the date of first administration of study drug.
- Concomitant: defined as medications/procedures administered during treatment period, between first and last administration of study drug.
- Post: defined as medications/procedures started after the date of last administration of study drug.

Details for handling of completely/partially missing dates are described in Section 8.1.2.

Prior and concomitant medications will be summarized by anatomical therapeutic chemical (ATC) levels 2, 4 and WHO drug preferred name. In case multiple ATC codes are assigned to a drug, all ATC-2nd level terms will be used for reporting.

In addition, a summary table will be provided describing:

- The number and percentage of subject with Sevelamer
- Time from treatment start to first administration of Sevelamer defined as date of start of Sevelamer use - date of first administration of the study drug +1. Missing day will be imputed as first day of month and missing month will be imputed as January. Completely missing date will not be imputed.
- Maximal dose of Sevelamer per subject
- The number and percentage of subject with Sevelamer, lanthanum carbonate and acetazolamide (Standardized term)

All medications and procedures date will also be listed.

Post-withdrawal anti-cancer treatments and any procedures will be listed and will include:

- Post-withdrawal radiotherapy: location, dose, start and end date, number of fraction days.
- Post-withdrawal anti-cancer therapy: therapy agent, therapy class, intent of therapy, line number, start and end date, reason for therapy.
- Procedures: procedure name/description, reason for procedure, if hospitalization was required, date of procedure.

[REDACTED]

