8.1.1 Adverse Event

When the day of onset of an AE is missing:

- If month and year of onset of an AE is the same as the month and year of date of first administration of the study drug:
 - If AE end date contains a full date and end date is earlier than study treatment start date, then the missing onset day is entered as the 1st of the month.
 - Otherwise, the missing onset day is entered as the day of date of first administration of the study drug.
- If month and year of onset of an AE is not the same as the month and year of date of first administration of the study drug, the missing onset day is entered as 1st of the month.

When the day and month of onset of an AE are missing:

- If year of onset of an AE is the same as the year of date of first administration of the study drug:

- If AE end date contains a full date and end date is earlier than study treatment start date, then the missing onset day and month are imputed as January 1st.
- Otherwise, the missing onset day and month are imputed as the day and month of date of first administration of the study drug
- If year of onset of an AE is not the same as the year of date of first administration of the study drug, the missing onset day and month are imputed as January 1st.

If AE onset date is completely missing:

- If AE end date is on or after the date of first administration of the study drug, then onset date is set to date of first administration of the study drug.
- If AE end date is prior to the date of first administration of the study drug, then onset date is not imputed, and AE is not considered as treatment-emergent.

If AE end date is prior to the date of first administration of the study drug, then onset date is not imputed, and AE is not considered as treatment-emergent.

If AE end day is missing, then end day will be imputed as last day of the month, or end date of the on-treatment period, whichever is earlier

If AE end day or month are missing, then end day will be imputed as last day of the month and end month will be imputed as December, or end date of the on-treatment period, whichever is earlier.

If AE end date is completely missing, then imputed as end date of the on-treatment period.

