8.1.2 Concomitant Medications

End date: Missing day will be imputed as the last day of the month, and missing month will be imputed as December.

Start date: Missing day will be imputed as the first day of the month, and missing month will be imputed by January. If the start date is completely missing, then:

- If the end date is prior to the date of first administration of the study drug, then the medication is considered as prior
- If the end date is prior to or on the date of last administration of the study drug, then the medication is considered as prior and concomitant
- If the end date is completely missing or after the date of last administration of the study drug, then the medication is considered as prior, concomitant and post.

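### Partial medication start dates are not bounded at first dose, so sevelamer begun on treatment can get a zero or negative time to start and an added prior flag

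*SAP*

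**What the plan says.** SAP 10.3.7 plans a summary of time to first sevelamer, calculated as "date of start of Sevelamer use - date of first administration of the study drug +1". For partial start dates it says "Missing day will be imputed as first day of month and missing month will be imputed as January", and for wholly absent ones "Completely missing date will not be imputed". It refers to SAP 8.1.2 for medication dates in general, where the rule is the same: "Start date: Missing day will be imputed as the first day of the month, and missing month will be imputed by January".

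SAP 10.3.7 then sorts medications by date. The first category is "Prior: defined as medications/procedures with start date before the date of first administration of study drug". The second is "Concomitant: defined as medications/procedures administered during treatment period, between first and last administration of study drug". These two can overlap, and 8.1.2 itself assigns both labels to one record in one of its cases.

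SAP 8.1.1 treats adverse events differently. If the day is missing and the month and year match those of first dose, onset goes to the 1st only when a full end date shows that the event was over before treatment. "Otherwise, the missing onset day is entered as the day of date of first administration of the study drug". A parallel rule covers day and month both missing in the first-dose year.

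SAP 8.1 adds that subject listings show incomplete dates as they were collected.

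**The concern.** In this trial sevelamer is on-treatment management of raised phosphate. Protocol Appendix E starts it at 5.5 mg/dL, and the first scheduled on-treatment phosphate check after Day 1 is Cycle 1 Day 8. A start in the same calendar month as first dose is therefore possible. If the day is then missing, imputing the 1st puts the start before the drug that prompted it, unless dosing began on the 1st.

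Two outputs are exposed. The time-to-sevelamer row can contain values that cannot occur for on-treatment use, including a day 0 that the study-day convention in SAP 9.2 does not have. The prior-medication summary can also gain binders that were not taken before the study. An adverse event and a medication with the same partial date would be handled inconsistently: the event is moved to first dose and its treatment to before first dose.

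**Working it through.** The plan gives no figure on this point, so there is none to reproduce. The check applies the SAP's own formula to example dates. All calendar dates and lags below are illustrative assumptions.

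**Inputs.** Time = start - first dose + 1 (SAP 10.3.7). Missing day = 1st, missing month = January (10.3.7, 8.1.2). Prior = start before first dose (10.3.7). The comparison rule is the bound at first dose in 8.1.1.

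**Day missing, start in the first-dose month.** If first dose is on calendar day d, the imputed time is 1 - d + 1 = 2 - d. This is 1 for dosing on the 1st, 0 on the 2nd, -1 on the 3rd, -13 on the 15th and -29 on the 31st. Any d of 2 or more also meets the prior definition.

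**Worked example.** First dose 20 March 2020, true sevelamer start 28 March.
- True time: 28 - 20 + 1 = 9.
- Day missing: 1 - 20 + 1 = -18.
- Day and month missing: 1 January is 79 days before 20 March 2020, so -79 + 1 = -78.

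**Day missing, start in a later month.** First dose 15 March, true start 10 April: the true time is 27 and the imputed time (1 April) is 18. It is too short but positive, and there is no prior flag.

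**How the effect depends on timing.** Taking every first-dose date in 2019 with equal weight, for a fixed true study day of sevelamer start:

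| True study day | Day missing: time < 0 | Day missing: classed prior | Day and month missing: time < 0 |
|---|---|---|---|
| 8 | 70.4% | 73.7% | 97.5% |
| 15 | 47.4% | 50.7% | 95.6% |
| 22 | 24.4% | 27.7% | 93.7% |
| 28 | 4.9% | 7.9% | 92.1% |
| 29 | 1.9% | 4.9% | 91.8% |
| 57 | 0% | 0% | 84.1% |
| 85 | 0% | 0% | 76.4% |

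These are shares of partial records, not of all sevelamer users. With day and month both missing, the lowest value is -356 days (true day 8).

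**Averaged scenario.** True start 7 to 27 days after first dose, each lag equally likely, day missing, all 2019 first-dose dates: 365 x 21 = 7,665 combinations.
- Start falls in the first-dose month: 44.1%.
- Imputed before first dose (time of 0 or less): 40.8%. Strictly negative: 37.5%. Exactly zero: 3.3%.
- Mean true time 18.0 days, mean imputed time 3.3 days, mean understatement 14.7 days.

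**With the 8.1.1-style bound.** The minimum time becomes 1 and no on-treatment start is imputed before first dose. In the worked example both -18 and -78 become 1, against a true 9. In the averaged scenario mean understatement falls from 14.7 to 11.4 days, so 11.4 / 14.7 = 78% of it remains.

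**The case against.** A reader might infer that on-treatment rescue is reported as pre-existing therapy instead of concomitant therapy. The documents do not support that. The concomitant category depends on administration between first and last dose, whatever the start date, so the record stays in the concomitant summary and gains a second label. Listings show the date as collected. The sevelamer counts carry no stated date condition, and lanthanum and acetazolamide have no time-to-start row, so for them only the extra prior flag is at issue.

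A reader might also infer that the fault is common, or that it shifts the reported median. Neither is shown. The documents give no distribution of time to sevelamer and no count of partial dates. The protocol requires administration dates in the eCRF (7.7.4) and provides for queries and source verification (11.2.1), so partial dates for a drug started in response to a laboratory value may be few. A handful need not move a median, although one large negative value would set the minimum and could pull the mean.

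The timing of the toxicity is also measured independently. SAP 10.3.3 summarizes time to phosphate of 5.5 mg/dL or higher from laboratory dates, which this rule does not touch, and no planned analysis links adverse-event onset to medication start.

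Finally, bounding at first dose leaves most of the early bias in place, because it dates same-month starts to Day 1. All of this stands and limits the reach of the point. It does not answer the core: the rule as written returns impossible times for some on-treatment starts, and the same SAP avoids this for adverse events.

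**Conclusion.** The point holds as a minor one. SAP 10.3.7 and 8.1.2 lack the first-dose bound that 8.1.1 has. The consequence is confined to partial dates whose known month (day missing) or year (day and month missing) matches that of first dose. There, on-treatment sevelamer can get a zero or negative time, and binders or acetazolamide can be flagged prior in addition to concomitant. Starts in later months with only the day missing are shortened but stay positive, and wholly missing dates are left alone.

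The size per affected record follows from arithmetic. The share of records affected cannot be known from the documents, and the percentages above rest on the assumed 2019 calendar and the assumed lags. One descriptive row and one descriptive summary are at stake; no endpoint, test or decision depends on them.

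**What to change.** In SAP 10.3.7 and 8.1.2, add the logic of 8.1.1. If the known month and year (day missing) or the known year (day and month missing) match those of first dose, and the end date is not before first dose, impute the later of the first of that period and the first-dose date. As in 8.1.1, an absent end date should not count as earlier. Otherwise keep the current rule. Footnote the time-to-sevelamer row with the number of imputed start dates, so that readers can judge the remaining bias.

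The cost is a sentence in each section, reuse of the adverse-event imputation code and one footnote. There are two downsides. A binder truly begun shortly before first dose, with a partial date, would be dated to Day 1; 8.1.1 already accepts the same trade-off for adverse events. The imputed times also remain biased early, by a mean of about 11.4 days in the assumed scenario, so the change should be described as removing impossible values and false prior flags, not as correcting the estimate.

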10.5 Pharmacokinetics

10.5.1 Debio 1347 Plasma concentration

Individual Debio 1347 plasma concentrations will be listed by cohort, gender, subject, and relative time from dosing on PK population, values will be presented as collected.

Concentrations will be summarized by timepoint according to time window specified in Table 4. Concentrations derived from samples taken outside of this time window will be considered as unscheduled, hence excluded from descriptive analysis. However, the derivation of PK parameters will not exclude those unscheduled samples since the actual time of sampling will be used instead of the nominal time. Invalid PK measurements (e.g. due to subject vomiting on the same date after dosing, or to sample collected after treatment interruption or dosing reduction and therefore not reflecting steady-state) will be excluded from analyses and flagged in the data listing.

Table 4 - Protocol specified time window for PK plasma sampling

Cycle	1		2	
Time point/Day	14	28	14	28
Pre-dose	● - 2 h	● -2 h	● -2 h	● -2 h
1 h post-dose		● ± 20 min		
3 h post-dose		● ± 30 min		● ± 30 min
7 h post-dose		● ± 30 min		

The following plots will be presented by time point for trough levels (i.e. pre-dose on Cycle 1 Day 14 and Day 28, Cycle 2 Day 14 and Day 28), concentrations at Cycle 1 Day 28 and Cycle 2 Day 28 separately. Unscheduled samples will not be presented in the figures:

- Arithmetic means ± arithmetic standard deviations using linear/linear scales
- Geometric means and 68% prediction interval using log₁₀/linear scales, where the 68% prediction interval is calculated as $\exp(\text{meanlog} \pm \text{SDlog})$ where meanlog and SDlog are mean and standard deviation of log-transformed concentration values.

10.5.2 Debio 1347 Pharmacokinetics parameters

Based on sparse sample plasma concentrations, PK parameters (C_{trough} , AUC_{τ} and any other PK parameters as deemed appropriate) will be derived by population PK data analysis using a nonlinear mixed-effects modelling approach. A Data Analysis Plan will be prepared for the dedicated population PK analysis and will be presented separately.

Individual plasma PK parameters will be presented in a by-subject listing, and summarized by cohort and overall using descriptive statistics.

If deemed appropriate depending on the safety and efficacy outcomes, covariate and exposure-response analyses may be conducted.

[REDACTED]

[REDACTED]

[REDACTED]

[REDACTED]

[REDACTED]

10.6 C-QTcF analysis

If deemed appropriate depending on the safety and efficacy outcomes and data availability, an exposure-response (C-QTcF) analysis may be performed as described below.

Concentration-response relationship will be investigated for change from baseline in QTcF from central reading and Debio 1347 plasma concentrations.

This study did not include a placebo control and no run-in period with ECG recording before dosing with study drug. Therefore, placebo effects on QTcF could not be evaluated and accounted for.

10.6.1 Graphical Exploration:

In order to assess quality of QTcF correction before and after dosing the following figures will be provided:

- Scatter plot of QTcF versus RR at baseline with a regression line.
- Scatter plot of change from baseline for QTcF versus change from baseline in RR for values collected during Debio 1347 treatment periods with a regression line.

In both cases, the regression lines should tend toward a horizontal line, otherwise, a dependency still exists between QTcF and RR and a study specific QT correction (QTcSS) may be considered as the preferred dependent variable.

The following exploratory plots will also be performed before starting the modelling:

- Scatterplot of individual change from baseline for QTc values vs. time-matched concentrations including a nonparametric trend curve will be provided to assess the pattern of the relationship.
- Scatterplot of individual change from baseline for HR values vs. time-matched concentrations including a nonparametric trend curve will be provided to detect impact of the treatment on HR.

10.6.2 Model Development

The model development will start with the pre-specified mixed linear model as detailed in Garnett et al. (2017) considering the change from baseline in QTcF as dependent variable. In case of the graphical exploration suggests that Fridericia correction does not account for all RR variation, change from baseline in QTcSS will be used as a sensitivity analysis.

The fixed effect parameters of the pre-specified model will be the intercept, slope for Debio 1347 concentrations, influence of baseline (centered on mean) on the intercept. Subject specific random effects will be added on the intercept and slope parameters with an unstructured covariance matrix. In the case that the unstructured covariance matrix is not supported by the data, other simplified or reduced structures will be investigated (ex. variance components). As no placebo group is included in the study, no time factor will be included in the model to account for circadian variations.

Additive effects on the intercept may be investigated, e.g. the effect of intrinsic factors (such as demographic, pathophysiological, or PGx characteristics if deemed appropriate) or extrinsic factors (such as concomitant medications).

10.6.3 Model Evaluation

Goodness of fit plots will be provided, consisting of:

- Quantile-quantile plots of residuals;
- Concentrations versus residuals;
- Time and baseline versus residuals;
- Any marked bias in residual plots may suggest model misspecification. In addition, structural model hypothesis will be checked from graphical exploratory plots;
- The absence of effect on HR will be investigated from time course of change from baseline for HR;
- The hypothesis of direct relationship will be evaluated from the time course of change from baseline for QTcF by cohort. If the central tendency analysis allows to reject the hypothesis of QT/QTcF prolongation, hysteresis phenomenon will not be considered, otherwise, hysteresis will be investigated by visual inspection comparing time of peaks in change from baseline for QTcF and concentrations;
- The hypothesis of linear relationship between change from baseline for QTcF and concentrations will be evaluated from exploratory scatter plots, the goodness of fit plots and will be supported by testing a quadratic concentration term in the model.

In case of the linear relationship between change from baseline for QTcF and Debio 1347 concentrations cannot be accepted, an alternative model such as saturable model will be considered.

10.6.4 Display of Results and Decision Rules

Parameters estimated from the selected model will be presented with their standard error and 95% CI.

Predicted change from baseline for QTcF at C_{max} geometric mean will be presented with their 2-sided 90% CI and a graphical display of predicted change from baseline for QTcF over the concentration range collected during the study will be provided.

The impact of Debio 1347 on QT/QTc prolongation will be considered as below the threshold of regulatory concern if the upper bound of the 90% CI of predicted change from baseline for QTcF at C_{max} is below the regulatory limit of 20 milliseconds, which is generally applied for oncology compounds (Maison-Blanche et al. (2013), Sarapa and Britto (2008)).

10.8 Interim Analyses

10.8.1 Planned interim analysis

This study will have IDMC analyses as described in IDMC Charter with focus on study safety, drug tolerability as well as efficacy.

As a part of IDMCs, an interim analysis will be conducted at end of Stage 1 to assess ORR homogeneity across baskets as well as futility. The testing will be conducted as per the schema provided in Figure 1.

The interim analysis will be performed at end of Stage 1 on the first 27 evaluable subjects i.e. subjects in the ITT who have at least 1 post-baseline tumor assessments or progressed.

Every effort will be made to ensure equal accrual rates between cohorts during Stage 1. In case of unequal accrual rates during stage 1, the interim analysis will be conducted when the slowest enrolling cohort will have a minimum of 4 evaluable subjects and the study has a minimum of 27 evaluable subjects with a maximum of 13 evaluable subjects in any of the other cohorts.

A feasibility assessment will be evaluated prior to assessment of homogeneity to ensure the recruitment feasibility in the targeted population. One or more cohorts may be stopped prematurely as a result of the feasibility assessment. The homogeneity will be assessed by comparing, across cohort, the ORR as assessed locally by investigator at the time of the data cut-off. ORR to be used in the homogeneity assessment will be defined as the proportion of subject with a BOR of confirmed or unconfirmed CR or PR as locally assessed by the investigator. The BOR will be derived using all disease assessments performed locally by investigator prior to the data cut-off. The homogeneity assessment will be performed by comparing the observed p-value for the Fisher’s exact test for 3x2 contingency tables to the pre-defined cut off value of 0.5. Homogeneity assumption will be rejected if the p-value generated is below 0.5. The cut-off value was determined as part of the simulations for sample size determination (see Section 6).

A futility assessment will be performed after the homogeneity assessment. Futility stopping rules are described in Table 5.

Table 5 - Futility stopping rules

Homogeneity assessment	Futility assessment sample	Futility stopping rule
Homogeneity met	All cohorts combined on first 27 evaluable subjects across cohorts	Stop study for futility if less than 3 responders If 3 or more responders, continue to Stage 2 and enroll the remaining subjects across all cohorts.
Homogeneity not met	First 9 evaluable subjects OR all evaluable subjects if cohort enrolled less than 9 subjects	Stop individual cohort for futility if 0 responder If 1 or more responders, cohort is eligible to continue into Stage 2.

Note: For homogeneity and futility assessment at the interim analysis, responder is defined as a subject with a BOR of confirmed or unconfirmed PR or CR based on investigator assessment.

In addition to the homogeneity and futility assessment procedure described above, the posterior probability of $ORR \geq 15\%$ in any of the cohorts will be provided to IDMC members as supportive information for their recommendation. Based on simulations, a cutoff of a posterior probability (of $ORR \geq 15\%$) less than 65% ($< 65\%$) in any of the cohorts, when used as a secondary assessment criteria for heterogeneity, provided improved operating characteristics (see Appendix in section 13.4). Posterior probability will be calculated using a uniform prior beta distribution with parameters 1 and 1.

If homogeneity is concluded at end of Stage 1, every effort will be made to ensure comparable enrolment rates between the three cohorts during Stage 2.

